#### Safety Endpoints

Excess weight gain (>1.5 lb/wk)

Change in and absolute values for several health outcomes including blood pressure, serum cholesterol, fasting and 24-hour glucose concentration and hydration status

Excessive muscle soreness and/or pain

Muscle or joint injury

General fatigue

## 5.0 Study Design and Statistical Analysis Plan

**5.1** *Describe the basic study design/approach (e.g., qualitative study using five focus groups of first year students to describe assimilation into the university community; randomized controlled trial of a behavioral change intervention to increase dietary intake of whole grains; pre- post-test evaluation of new pedagogical techniques to improve adult literacy):*

This study is a randomly assigned intervention study that will evaluate the effect of a 10-wk diet and exercise regimen designed to promote healthy weight gain in athletes and military personnel (who desire weight gain). This will include increasing energy intake by 500 additional kcal/day (above weight maintenance diet) through daily provision of either peanut-based whole foods/snacks (peanut group) or a similar, high-carbohydrate, peanut-free snack (control group) along with a supervised resistance training regimen.

*5.2 Describe corresponding data analysis plan/approach (e.g., content analysis of focus group transcripts; descriptive analysis followed by linear regression modeling; nonparametric analysis of pre- and post-test measures):*

Data will be analyzed using IBM SPSS statistics software. Repeated measures ANOVA will be used to assess changes in dependent variables including participant body weight, body composition and anthropometric variables by group and across time (Aim 1). Student t-tests and simple and partial correlation statistics (Pearson Product or Spearman Rank) will be used to evaluate the magnitude of change in body weight/lean mass according to participant characteristics (sex, age, training status, somatotype) and significant adaptive changes in thermogenesis and appetite (Aim 3). Descriptive statistic methodologies will be applied to evaluate the ease and acceptability of peanut foods in the weight gain meal plan (Aim 2). The significance level will be set a priori at  $p < 0.05$

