6	7 April	We added abnormal serum lipids as an exclusion criterion (section 12.0, page 26). We added an additional questionnaire at baseline to evaluate vitamin D status as a baseline health outcome and a study exit survey at study conclusion (Table 1 and section 8.2). We clarified that we will also measure iodine concentration in the urine samples to help interpret thyroid and other hormone concentrations at baseline and study end. We would also like to increase our potential sample size to 40 from 32 to account for a possibility of drop outs and ensure we have a complete sample of 32 participants; we still plan on recruiting as close to half men and half women as possible with a balance between our two intervention groups. We also added an exit survey. We uploaded the Vitamin D Food Frequency and Lifestyle Questionnaire and the Exit Survey.	Yes

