## **7.0 Study Intervention(s)/Investigational Agent(s)**

*7.1 Describe the study interventions (including behavioral interventions) and/or investigational agents (e.g., drugs or devices) to be used in this study. Consider each of the items listed below:*

- *Drug/Device Handling: If the research involves drugs or devices, describe your plans to store, handle, and administer the drugs or devices so that they will be used only on subjects, and only by authorized investigators.*
- *Describe whether any of the following will be used: microwaves, X-rays, DEXA scans, general anesthesia, or sedation*
- *If control of the drugs or devices used in this protocol will be accomplished by following an established, approved organizational SOP (e.g., Research Pharmacy SOP for the Control of Investigational Drugs, etc.), please reference the SOP in this section.*

The Research does not involve administration of drugs. The research does involve use of Dual-energy x-ray absorptiometry (DXA/DEXA) scans that will be performed at 4 timepoints during the study

*7.2 List the name of all drugs (including any vitamins, supplements, herbs, or nicotine) to be used in the study. Indicate whether they have FDA approval, and list any limitations for their use:*

N/A

*7.3 List all devices, how they will be used, their purpose in the study, and if they will be used in a manner consistent with their approved uses. If they will be used in ways that are not yet FDA approved, indicate whether they need an IDE or a determination that they are exempt from the IDE Determination. If a determination of significant risk or non-significant risk is needed for any of the devices, include the researcher's recommendation for each of those devices:*

The medical devices/equipment used in this study include the DXA and the CGM sensors.

The DXA will be used to assess total body composition. Both devices are FDA approved and the research will involve employment of these devices for approved uses. Scans will be performed only by members of the research staff who are trained and certified bone densitometry

technologists (CBDT) through the International Society of Clinical Densitometry.

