## 14.0 Number of Subjects

14.1 *Indicate the total number of subjects to be enrolled and how this number was determined (e.g., sample size calculation [show], number of available subjects in a finite pool, number of tests funding award would allow):*

The sample target of 16 men and 16 women was selected because we believed it would be feasible to recruit and study this number within the time frame and budget set by the funding agency. We, however, will target recruitment of up to 40 participants. Based on limited previous studies in men who have used a range of 12 to 46 subjects, we also believe this number is sufficient to show measurable results.

14.2 *If this is a multi-site study, indicate the number of subjects to be enrolled at this site and the total to be enrolled from all sites:*

N/A

*14.3 If applicable, indicate the number of potential subjects you expect to screen for enrollment, and the number of subjects you will need to complete the research procedures:*

We anticipate that we may need to screen between 100 and 150 participants to recruit and complete the required 32 participants.

*14.4 If the study has more than one procedure, indicate the total number of subjects to undergo each procedure separately:*

20 participants (~10 men/10 women) will be assigned to the peanut-containing snack group and 20 participants (~10 men/10 women) will be assigned to the control snack group as previously mentioned.

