## **16.0 Withdrawal of Subjects**

*16.1 Describe circumstances under which you anticipate subjects could be withdrawn from the research without their consent:*

Participants could be withdrawn from the study if they are not showing up for appointments and/or training sessions, are not consuming the provided snacks, or are not completing or complying with all procedures. They also may be withdrawn if they develop an injury or illness that would prevent

them from doing everything that is expected for the study or which might compromise their health.

*16.2 If applicable, describe any procedures for orderly termination (e.g., discontinuation of a study drug or debriefing after a behavioral intervention):*

If a participant is not complying with the study, the PI or study coordinator will first discuss these difficulties with the participant and explain the importance of adhering to the intervention for the purpose of the study. If it is determined that the participant be terminated or discontinued from the study for reasons as described above, the PI will mitigate issues leading to these problems. The participant will be provided any information which is available to them (baseline body composition, fitness testing, resting metabolic rate). It will then be suggested that the study personnel part ways with the participant

*16.3 Describe procedures that you will follow when subjects withdraw from the research, including partial withdrawal from procedures with continued data collection (e.g., participant declines to continue with regular blood draws, but continues with periodic behavioral questionnaires):*

Any participant can discontinue participation at any point without consequence.

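### The planned repeated-measures ANOVA, in its usual SPSS form, drops anyone who misses a visit, and the plan has no rule for missed visits; a mixed model would use all the data

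*Combined protocol and SAP*

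**What the plan says.** Section 5.2 is the whole analysis plan. For Aim 1 it states: "Repeated measures ANOVA will be used to assess changes in dependent variables including participant body weight", and goes on to body composition and anthropometry, compared by group and over time. On software it says: "Data will be analyzed using IBM SPSS statistics software". It names no SPSS procedure, no analysis set and no rule for missed visits, and it mentions neither imputation nor a mixed model.

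Table 1 schedules weight and DXA at baseline and weeks 3, 7 and 11. Section 7.1 likewise describes DXA "scans that will be performed at 4 timepoints during the study". Skinfolds and circumferences are taken only at baseline and week 11.

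On drop-out, revision 6 in the revision history raised the possible sample from 32 to 40 to "account for a possibility of drop outs and ensure we have a complete sample of 32 participants". Section 14.1 targets up to 40, and Section 14.3 expects to screen 100 to 150 people "to recruit and complete the required 32 participants". No drop-out rate is given. Section 16.1 lists among the grounds for withdrawal without consent that participants "are not consuming the provided snacks, or are not completing or complying with all procedures". The template question in Section 16.3 asks about partial withdrawal with continued data collection. The answer says only that anyone may stop without consequence.

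**The concern.** Classical repeated-measures ANOVA needs a value at every visit. Run as SPSS GLM Repeated Measures, it removes a participant with one missing weight, however many others were recorded. That has two consequences.

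- **Waste.** Weights and scans already collected before a withdrawal, or around one missed interim visit, would not be used.
- **Bias.** The analysis would describe completers only, which is safe only if those who leave resemble those who stay. Not eating the surplus snacks is plausibly linked to low gain. If low gainers leave, mean gain is overstated, and an average gain of 1/2 lb a week is itself a hypothesis in Section 2.2. If they leave one arm more often, the arm difference is biased too.

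The protocol supplies a possible route to unequal loss. Section 2.2 expects the peanut snacks to be better accepted. If that is right, more control participants might meet the snack criterion in Section 16.1. Removing them would raise the control mean among completers and shrink the difference being sought.

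**Working it through.** **1. The plan's own figures.** There is no power calculation, effect size or SD to reproduce; Section 14.1 rests on feasibility. The only link is 1 − 32/40 = 20% loss, which is implied by the two numbers and not stated.

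**2. Data discarded.** If 8 of 40 leave, the visits dropped per outcome, as a share of all observed visits, are:
- after baseline: 8/(32×4 + 8) = 8/136 = 6%
- after week 3: 16/144 = 11%
- after week 7: 24/152 = 16%

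Scattered misses cost whole participants. If each of three follow-up visits is missed independently with probability m, 40(1 − m)³ remain: 36.5, 34.3 and 29.2 at m = 3%, 5% and 10%.

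**3. Effect on the estimates.** All inputs here are assumptions: 20 per arm; gains of 0.5 and 0.4 lb/week over 10 weeks (true difference 5.0 − 4.0 = 1.0 lb, overall mean 4.5 lb); between-person slope SD 0.25 lb/week; residual SD 1 lb; on average 20% lost after week 7.

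Hand check, with the lowest week-7 gainers leaving:
- SD at week 7 = √((0.25×7)² + 1²) = 2.016
- Covariance of week-7 and final gain = 0.25²×7×10 = 4.375; ratio 4.375/2.016 = 2.17
- Removing the lowest fraction p raises the mean of those left by φ(z_p)/(1 − p) SDs: 0.497 for 30%, 0.350 for 20%, 0.195 for 10%
- 30% lost in control and 10% in peanut: 1.0 − 2.17×(0.497 − 0.195) = 0.34 lb
- 20% lost in each arm: difference stays 1.0 lb; mean gain 4.5 + 2.17×0.350 = 5.26 lb

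Simulation agrees and shows how far the result depends on the loss pattern:

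| Loss pattern (control vs peanut) | Completer difference (truth 1.0 lb) |
|---|---|
| Lowest gainers leave, 30% vs 10% | 0.30 to 0.37 |
| Low gainers more likely to leave (odds ×2.7 per SD), 30% vs 10% | 0.57 |
| Lowest gainers leave, 30% vs 10%, slope SD 0.15 | 0.68 |
| Lowest gainers leave, 25% vs 15% | 0.69 |
| Odds ×2.7 per SD, 25% vs 15% | 0.79 |
| Odds ×1.6 per SD, 25% vs 15% | 0.86 |
| Equal or random loss | about 1.0 |

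A likelihood estimate using all visits gives 1.00 to 1.01 lb in the first row. With equal loss of the lowest gainers, completer mean gain is 5.2 to 5.3 lb against 4.5 lb. With probabilistic loss the overstatement is 0.2 to 0.4 lb, so 4.7 to 4.9 lb. With random loss the SD of the difference is 0.95 for completers and 0.89 using all visits: 1 − 0.89²/0.95² = 12% less variance.

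**4. A second set of assumptions.** No true difference, 0.5 lb/week in both arms, SD of final change 2 to 4 lb, about 20% lost after week 3. Completer bias is about 0 if loss is random or follows the same pattern in both arms. It is −0.32 to −1.03 lb if low gainers leave one arm and high gainers the other, with type I error of 7 to 11%. It is −0.40 to −1.28 lb if only one arm loses people, mostly low gainers, with type I error of 8 to 14%. Using all visits keeps bias between −0.03 and +0.04 lb throughout.

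**5. Where the mixed model falls short.** If leaving follows a participant's underlying rate of gain instead of the gain recorded so far, completers give 0.25 lb and the likelihood estimate about 0.7 to 0.8 lb. Under equal loss its mean gain is about 4.8 lb, not 4.5 lb.

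**The case against.** A reader might infer that the plan commits to discarding partial data. It does not. Section 5.2 names a method and a software package but no procedure, and the complete sample of 32 is a recruitment target. Dropping incomplete participants is a property of the method's usual form, not a stated rule.

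A reader might also infer that Section 16.1 makes unequal loss likely. It says participants could be withdrawn, also for missed sessions, injury or illness, and mentions neither weight gain nor arm. Drop-out is described only as possible, and the protocol works against it: $150 of the $200 payment depends on the final visit and at least 85% of sessions, progress is checked weekly, and problems are discussed before anyone is terminated.

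The largest figure is close to a worst case, since it removes exactly the lowest gainers at three times the rate in one arm. Even then the bias (1.00 − 0.37 = 0.63 lb) is smaller than one SD of the estimate, about 0.9 lb.

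These points stand and limit the certainty and size of the concern. They do not supply a rule for a participant with three of four weights, and the method as named gives a poor default.

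**Conclusion.** The concern holds in a conditional form. Section 5.2 names a method whose usual form excludes anyone missing a visit, for outcomes measured four times, and nothing elsewhere in the protocol repairs this. Three outcomes follow under the assumed values:

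- **Arm difference:** about 0.3 to 0.9 lb against a true 1.0 lb if low gainers leave one arm more often; no bias if loss is random or follows the same pattern in both arms.
- **Mean gain:** about 4.7 to 5.3 lb against 4.5 lb if low gainers leave, even when the arms lose equally.
- **Precision:** about 12% of variance given away if loss is random.

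The loss rate, its dependence on gain, its imbalance by arm and the SDs are all assumptions; the documents give none of them. It would be too strong to say that the arm comparison will be biased, or that a mixed model would remove all bias. The model does so only when leaving depends on observed values, and withdrawal for non-adherence may not meet that condition fully. Skinfolds and circumferences are unaffected by a missed week-3 or week-7 visit.

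**What to change.** In Section 5.2, for outcomes measured at more than two visits (weight, DXA fat-free mass and fat mass), replace the repeated-measures ANOVA with a linear mixed model for repeated measures (SPSS MIXED):

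- fixed effects for arm, visit, arm-by-visit, baseline value and sex, because Section 8.1 randomises each sex separately;
- unstructured covariance over the three follow-up visits (3×4/2 = 6 parameters) and small-sample degrees of freedom;
- all randomised participants with any post-baseline value, analysed as assigned;
- the week-11 arm difference as the reported estimate.

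Report drop-out by arm with reasons, including anyone who leaves before week 3 and so has no post-baseline value. Keep the completer ANOVA as a sensitivity analysis, and add one sensitivity analysis for loss not explained by observed data.

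The cost is one paragraph and slightly more analysis work, with the same software and data.

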### 2.2 *State the hypotheses to be tested:*

The standard hypercaloric sports performance diet (500 kcal surplus energy, adequate protein and carbohydrate, judicious fat) and resistance training regimen with excess calories from peanut foods or high-carbohydrate snack foods will result in an average weight gain of 1/2 pound/week in both men and women, with the majority of that gain as lean (fat-free mass) mass.

Weight gain will be more efficient when the excess calories are from peanut foods (compared to control, high-carbohydrate foods) which will be better accepted than the control snacks.

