## 8.0 Procedures Involved

### 8.1 Describe and explain the study design:

Sixteen men and sixteen women between the ages of 18 and 40 will be randomly assigned to the peanut intervention or control group (8 men/8 women/group). A computer program with a random number generator will be used by the study coordinator to assign male participants and female participants to the peanut or control group (i.e., each sex will be separately randomized).

As outlined in the table, eligible participants will undergo a 10-wk diet and training regimen designed to promote healthy weight gain. This will include increasing energy intake by 500 additional kcal/day (above their typical weight maintenance diet and accounting for energy requirements of resistance training) through provision of peanut-based whole foods/snacks or high-carbohydrate containing control snacks along

with a supervised rigorous resistance training regimen designed to promote muscle hypertrophy. After providing informed consent, participants will be randomly assigned to the peanut or control group based on sex. Outcome data will include assessment of body mass, total and regional body composition via DXA and body anthropometrics, skinfolds and somatotyping using the International Standards for Anthropometric Assessment (ISAK) (Stewart, Marfell-Jones et al. 2011) along with measures of resting metabolic rate (RMR), circulating hormones and serum/plasma biomarkers. The latter includes measurement of potentially important hormones/ biomarkers of anabolism, stress, overfeeding, and cardiometabolic health. Compliance to the nutrition and exercise regimen will be evaluated at regular intervals and include collection of 3-day food records (performed at baseline and 3-days prior to each assessment point) and physical activity data collected by digital technology (Garmin Vena SQ smart watch and My PT Hub app).

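### Exploratory Aim 3 plans simple correlations of gain on participant traits without tying them to sex, so a sex-linked trait can appear to predict gain if gain also differs by sex

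*Combined protocol and SAP*

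**What the plan says.** Section 5.2 gives Aim 3 one sentence of method: t-tests and "simple and partial correlation statistics (Pearson Product or Spearman Rank) will be used to evaluate the magnitude of change in body weight/lean mass". The factors examined are age, somatotype, training status and sex itself, together with adaptive changes in thermogenesis and appetite. The sentence does not say which variables the partial correlations control for, or whether any correlation is run within sex. The section then adds "The significance level will be set a priori at" p < 0.05, with no separate rule for Aim 3.

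Section 8.1 fixes the sex mix: "Sixteen men and sixteen women between the ages of 18 and 40 will be randomly assigned", with each sex randomised separately. Section 14.1 adds: "We, however, will target recruitment of up to 40 participants". The number of participants was chosen because it was "feasible to recruit and study this number within the time frame and budget", so no effect size, SD or power is given for any aim.

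Two other places bear on the point. Section 2.2 hypothesises that the regimen "will result in an average weight gain of 1/2 pound/week in both men and women", most of it lean, without giving a lean amount for either sex. Section 1.0 labels Aim 3 exploratory.

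**The concern.** A simple correlation computed across men and women together mixes two things: the association among people of the same sex, and the gap between the male and female averages. If men and women differ on average in both the trait and the gain, the gap alone produces a correlation. A balanced mix of the sexes gives that gap its greatest weight.

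Aim 3 asks which characteristics go with gain. A reader shown a significant simple correlation between, say, a somatotype component and lean gain would take it as information about somatotype, when it could be no more than a restatement of sex. The plan lists sex as one characteristic among several and does not use it as a control for the others. The partial correlations could supply that control, but the text does not commit them to it, and the simple correlations fall under the same significance level.

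**Working it through.** The plan gives no figure for Aim 3 to reproduce, so the check is of the mechanism and its size.

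**Inputs from the protocol.** 16 men and 16 women (8.1), or up to 40 participants, about 20 per sex (14.1, 14.4); significance level 0.05 (5.2).

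**Assumptions.** The documents give no sex differences or SDs. Let d_t and d_g be the male-female differences in trait and gain, in within-sex SD units. Assume continuous, normally distributed variables with equal SDs, no association within either sex, and two-sided Pearson tests. Spearman was not simulated.

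**Induced correlation.** In a 50:50 mix, the pooled covariance is d_t·d_g/4 and the pooled variances are 1 + d_t²/4 and 1 + d_g²/4. Hence

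r = [d_t/√(d_t² + 4)] × [d_g/√(d_g² + 4)].

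- d_t = 1, d_g = 0.5: 0.447 × 0.243 = 0.108
- d_t = 2, d_g = 0.5: 0.707 × 0.243 = 0.171
- d_t = 1, d_g = 1: 0.447 × 0.447 = 0.200
- d_t = 2, d_g = 1: 0.707 × 0.447 = 0.316
- d_g = 0, any d_t: r = 0

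**False-positive rate of the simple correlation**, from 20,000 simulated trials per row (per cell in the first row). The Monte Carlo standard error at 5% is √(0.05 × 0.95/20,000), about 0.15 percentage points.

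| Sex difference in gain (SD) | Sex difference in trait (SD) | Induced r | n = 32 | n = 40 |
|---|---|---|---|---|
| 0 | 0.5 to 3 | 0 | 4.6–5.2% | 4.9–5.1% |
| 0.5 | 1 | 0.108 | 8.8% | 10.5% |
| 0.5 | 2 | 0.171 | 15.6% | 18.9% |
| 1 | 1 | 0.200 | 20.3% | 24.3% |
| 1 | 2 | 0.316 | 44.5% | 55.0% |

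Recruiting more people makes this worse, because the induced correlation stays put while the critical value falls from 0.349 at n = 32 to 0.312 at n = 40.

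**With sex controlled.** The partial correlation given sex rejects in 4.7% to 5.4% of trials in every scenario run (d_t from 0.5 to 3, d_g from 0 to 2, both sample sizes). At n = 32 it uses 29 degrees of freedom instead of 30, and the critical |r| moves from 0.349 to 0.355.

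**Which outcome is exposed.** Section 2.2 implies 0.5 lb × 10 weeks = 5 lb in each sex. If that holds, d_g = 0 for weight and the first row applies. For lean mass it says only that most of the gain is lean. Anything from just over 2.5 lb to 5 lb fits that statement in either sex, so a sex difference in lean gain is compatible with the hypothesis.

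**The case against.** The case for leaving the text alone has real weight. The plan does include partial correlation, in the same sentence that lists sex as a characteristic, and reporting simple correlations beside partial ones is ordinary practice. Aim 3 is exploratory, and the treatment comparison in Aim 1 uses repeated measures ANOVA and does not depend on it. The size of the problem rests on sex differences that no document supplies. All of this stands, and it limits the point to what the partial correlations control for and which result carries the inference.

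A reader might go further in three ways that the documents do not support.

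- **That every trait differing by sex will appear to predict gain.** Gain must differ by sex too. Under the section 2.2 hypothesis for weight there is no inflation, and even with moderate differences in both, most trials give no false positive.
- **That the plan states a pooled analysis.** It does not. Pooling is the natural reading where no within-sex analysis is mentioned, but it is an inference.
- **That the t-test by sex is wrong because it ignores body size.** Section 5.2 gives no unit or scale for that comparison. An absolute comparison would suit a protocol whose hypothesis, weekly goal and excess-gain limit are all in pounds, and whose 500 kcal/day surplus is initially the same for everyone. Body size can contribute to an absolute difference: an equal 3% gain with a 15 to 20 kg sex difference in weight (both assumed) gives 0.45 to 0.60 kg. That is a matter of interpretation and not an error. Using baseline lean mass as a covariate is itself debatable if the sexes overlap little on it.

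**Conclusion.** The point holds as a conditional weakness in an exploratory analysis. Section 5.2 leaves the control variable of the partial correlations unstated and plans simple correlations in a half-male, half-female sample. Where gain and trait both differ by sex, the simple correlation can name a predictor that has no association with gain within either sex. At n = 32 the false-positive rate is about 9% to 45% for assumed differences of 0.5 to 1 SD in gain and 1 to 2 SD in the trait, and about 5% if gain does not differ by sex. The figures also assume normal variables, equal SDs and two-sided Pearson tests.

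The concern is most plausible for lean mass and is not expected for weight if the protocol's own hypothesis is right. That hypothesis is not a safeguard, however, since Aim 3 examines sex as a factor and so treats its effect as open. The primary comparison is unaffected. The change is worth making because the remedy is nearly free and is best settled before the data are seen.

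**What to change.** In section 5.2:

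- State that for every Aim 3 trait other than sex, the inferential analysis is the partial correlation controlling for sex, or a linear model of gain on the trait with sex included.
- Keep the simple correlations as descriptive results only, without significance claims.
- Mark each scatterplot of gain against a trait by sex.
- Optionally, show percentage gain by sex beside the absolute gain, as description.

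This is a wording change. Sex, weight and body composition are already collected, so no procedure or visit changes. The statistical cost is one degree of freedom per analysis.

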## 1.0 Study Summary

Study Title	Exploring the Role of Peanuts in Enhancing Healthy Weight Gain in Athletic Individuals
Study Design	Randomly Assigned Intervention Study
Primary Objective	Determine the efficacy of the standard hypercaloric sports performance diet (500 kcal surplus energy, adequate protein and carbohydrate, judicious fat) and weight training regimen with excess calories from peanut foods or high-carbohydrate snack foods on weight and lean mass gains over 10 weeks in athletic men and women desiring weight gain.
Secondary Objective(s)	Secondary Aim: Evaluate the ease and acceptability of whole peanuts, peanut butter and peanut-based healthy snacks relative to high-carbohydrate snacks as part of the standard hypercaloric regimen. Exploratory Aim: Examine the effect of potential adaptive factors (increased resting metabolism, decreased appetite) and individual characteristics (sex, age, training history, somatotype) on weight and lean mass gains.
Study Population	Athletic and military men and women who desire weight gain primarily as lean mass to improve performance and/or effectiveness in sport/military endeavors.
Sample Size	32 (16 men and 16 women)
Research Intervention(s)/ Investigational Agent(s)	Men and women will be randomly assigned to a peanut intervention or control group (8 men and 8 women per group); Each group will undergo a 10-wk diet and weight training regimen designed to promote healthy weight gain.
Study Duration for Individual Participants	12 to 13 weeks including screening, baseline testing, the 10-week intervention and post-testing
Acronyms and Definitions	DXA, Dual-Energy X-ray Absorptiometry; TSH, thyroid-stimulating hormone; CBC, complete blood count; RMR, resting metabolic rate; REE, resting energy expenditure; VO 2 max, maximal oxygen uptake during exercise, also known as aerobic capacity; Reps; repetitions; CGM, continuous glucose monitoring; ISAK, International Standards for Anthropometric Assessment; ACSM, American College of Sports Medicine; IUSCA, International Universities Strength and Conditioning Association; HIP Laboratory, Human Integrated Physiology Laboratory; NEM Laboratory, Nutrition and Exercise Metabolism Laboratory

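### Aim 3 relates gain only to 'significant' changes in resting metabolism and appetite, and does not name the randomised arm as a covariate; a wording change fixes both

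*Combined protocol and SAP*

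**What the plan says.** Section 1.0 labels the aim exploratory: "Exploratory Aim: Examine the effect of potential adaptive factors (increased resting metabolism, decreased appetite", together with individual characteristics, on weight and lean mass gains. Section 2.1 repeats it. Neither section requires a factor to be significant before it is examined.

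Section 5.2 gives the methods: "Student t-tests and simple and partial correlation statistics (Pearson Product or Spearman Rank) will be used" to evaluate the size of the gain "according to participant characteristics (sex, age, training status, somatotype" and also according to "significant adaptive changes in thermogenesis and appetite (Aim 3". The word 'significant' qualifies the adaptive changes only. No test, contrast or time point defines it. The paragraph ends with "The significance level will be set a priori at" p < 0.05.

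Group appears once in the analysis plan, for the repeated measures ANOVA: "by group and across time (Aim 1". The variables to be partialled out in the Aim 3 partial correlations are not named.

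The planned sample in section 1.0 is "32 (16 men and 16 women". Section 14.1 allows recruitment of up to 40 and rests the number mainly on feasibility, without a power calculation.

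**The concern.** Two things in section 5.2 work against its own aim.

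The first is the significance condition. Whether mean resting metabolic rate (RMR) or appetite changed is one question. Whether participants whose RMR rose more, or whose appetite fell more, gained less is another. If some participants rise and others fall, the mean change can be zero while the association with gain is strong. The condition would then remove the measure before its association is examined. Because the test is undefined, which measures are carried forward could also be settled after the data are seen: Table 1 in section 8.1 schedules RMR at baseline and weeks 3 and 11, and appetite at baseline and weeks 3, 7 and 11, so several contrasts are available.

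The second is the arm. RMR change and appetite change are measured after randomisation, so the snack can shift them. Section 2.2 expects the arms to differ in efficiency of weight gain, and section 8.2 gives the snacks different protein contents (15 g against about 5 g). If arm moves both the adaptive measure and the gain, a correlation across all participants mixes the diet effect with individual adaptation. It can create an association that is absent within arms, or hide one that is present.

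**Working it through.** The documents give no power figure for Aim 3, so there is nothing to reproduce. The inputs taken from them are n = 32 (section 1.0), n = 40 as the recruitment ceiling (section 14.1), 1:1 allocation within sex (section 8.1) and a 0.05 level (section 5.2). Assumptions: two-sided tests, a paired t-test as the meaning of 'significant', normal data, and all effect sizes, which are in SD units and shown as ranges.

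**1. How often the condition drops a measure.** For a mean change of d SD, the paired t statistic is noncentral t with n − 1 degrees of freedom and noncentrality d√n. For n = 32 and d = 0.3 the noncentrality is 0.3 × 5.657 = 1.697 against a critical value of 2.040. That gives a pass rate of 0.376, so the measure is dropped 62% of the time.

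| Mean change (SD) | Dropped, n = 32 | Dropped, n = 40 |
|---|---|---|
| 0 | 95% | 95% |
| 0.2 | 80% | 77% |
| 0.3 | 62% | 54% |
| 0.5 | 22% | 13% |

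**2. What an unfiltered analysis could see.** By the Fisher z approximation, power for a true correlation r is Φ(arctanh(r)·√(n − 3) − 1.960). For r = 0.5 and n = 32 this is Φ(0.549 × 5.385 − 1.960) = Φ(0.998) = 84%. For n = 40 it is Φ(0.549 × 6.083 − 1.960) = 92%. An association of this size would usually be found if it were tested, but with no mean shift it would be tested only 5% of the time.

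**3. False association from arm.** Suppose the adaptive change and the gain are unrelated within arms and arm shifts both by d SD in the same direction. The correlation induced across all participants is (d²/4)/(1 + d²/4); for d = 0.8 that is 0.16/1.16 = 0.138. Rejection rates from 40,000 simulated trials:

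| Arm shift on both (SD) | Induced r | Simple correlation, n = 32 | Simple correlation, n = 40 | Partial given arm |
|---|---|---|---|---|
| 0.3 | 0.022 | 5.1% | 5.1% | 4.9% |
| 0.5 | 0.059 | 6.3% | 6.3% | 5.0–5.1% |
| 0.8 | 0.138 | 11.9% | 13.6% | 4.9% |
| 1.0 | 0.200 | 20.0% | 24.0% | 5.0% |

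**4. Masking.** Suppose the true within-arm correlation is 0.5 and arm shifts the two variables by d SD in opposite directions. The correlation across all participants becomes (0.5 − d²/4)/(1 + d²/4). For d = 0.5 this is 0.4375/1.0625 = 0.41, and for d = 0.8 it is 0.34/1.16 = 0.29. In simulation at n = 32, power of the simple correlation is about 66% and 36% respectively, against about 84% with arm partialled out.

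**The case against.** The plan can be defended on several grounds, and much of the defence stands.

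- A reader might infer that arm is left out of Aim 3. The text does not say so. Partial correlations are planned and their covariates are unnamed, so arm is unspecified, not excluded. The simple correlations, planned alongside them, do not adjust for it.
- A reader might infer that candidate moderators can be dropped or confounded. They cannot. Sex, age, training status and somatotype carry no significance condition. They are baseline variables, with sex balanced by separate randomisation and the others balanced in expectation, so an arm effect on gain does not confound their relation to gain.
- A reader might infer that pooling the arms generally inflates false positives. At same-direction shifts of 0.5 SD or less the rate stays near 5–6%; material inflation needs large shifts in both variables. The documents give no arm effect on RMR or appetite, and section 2.2 predicts differences in efficiency of gain and in snack acceptance only.
- 'Significant' could mean notable, and sections 1.0 and 2.1 state the aim without it. With p < 0.05 set in the same paragraph, however, the statistical reading is the natural one, and a looser reading leaves the selection just as undefined.
- RMR change and appetite change are secondary endpoints in section 4.1. The condition threatens only their analysis against gain, not their place as endpoints.

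This narrows the point without removing it. No reading makes a significant mean change a sensible precondition for studying individual association, and masking by opposite shifts matters at moderate effect sizes too.

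**Conclusion.** The concern holds for two measures, change in RMR and change in appetite. The significance condition answers a different question from Aim 3 and would often remove a measure before its relation to gain is examined: 62% of the time at a mean shift of 0.3 SD with 32 participants, and 95% at no shift. These figures assume that 'significant' means a paired t-test at two-sided 0.05. The missing arm adjustment is a gap in specification. Its effect on false positives is negligible at shifts of 0.3–0.5 SD and reaches 12–20% at 0.8–1.0 SD; opposite shifts of 0.5 and 0.8 SD cut power from about 84% to about 66% and 36%. All these shifts are assumed.

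The severity is minor. The aim is exploratory and the randomised comparison under Aim 1 is untouched. This is a cheap improvement, not a threat to the trial's main conclusion.

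**What to change.** In section 5.2, delete 'significant' before the adaptive changes and add:

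> *Change in RMR and change in appetite will each be related to change in weight and in fat-free mass regardless of whether the mean change is significant, using partial correlation (or regression) with arm and sex as covariates. All estimates will be reported with 95% confidence intervals as exploratory.*

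Also state which visits define each change. Sex is included because it is the randomisation stratum. The analyses of sex, age, training status and somatotype may stay as planned, and partial correlation keeps the chosen methods and software.

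The cost is wording and two degrees of freedom (30 to 28 for a correlation with 32 participants). No new data or visits are needed.
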